3. INVESTIGATIONAL PLAN

Study TAF116564 is a prospective, double-blind, double-dummy, multicenter, comparative study, enrolling 300 subjects and consisting of a 3 day in-patient hospital stay and 11 further on-treatment and follow-up study visits distributed over 180 days. The study schematic diagram in Section 3.1 summarizes the study visits.

3.1. Study Design Schema

CQ/TQ = Chloroquine 600mg OD Days 1 & 2; 300mg OD Day 3 / Tafenoquine 300mg single dose Day 2

CQ/PQ = Chloroquine 600mg OD Days 1 & 2; 300mg OD Day 3 / Primaquine 15mg OD Days 2-15

3.2. Study Design

- Study TAF116564 is a prospective, double-blind, double-dummy, multicenter, comparative study.
- A total of 300 subjects will be randomized 2:1 to receive TQ/CQ or the active comparator PQ/CQ. All subjects will receive CQ on Days 1 to 3 followed by TQ or PQ and matching placebo beginning on Day 1 or 2. Tafenoquine, or matching placebo, will be given as a single, 300mg dose. Subjects will receive PQ (15mg once daily) or matching placebo for 14 days.
- The duration of the study is 180 days, including screening and randomization to treatment (Day 1), three in-hospital days (Days 1-3), four out-patient visits while on treatment with study medication (Days 5, 8, 11 and 15) and seven follow-up visits (Days 22, 29, 60, 90, 120, 150 and 180).
- Subjects must have a blood smear that is positive for *P. vivax* at entry. Blood smears will be taken for parasitological assessment twice a day for the first 3 days of the study, or until two consecutive thick blood smears are negative for *P. vivax*. Additional parasitological assessments will be conducted throughout the treatment and follow-up periods.
- Subjects are required to remain in the hospital for the first three days of the study, in order to ensure clinical improvement, to monitor early study medication compliance, and so that parasitological assessments can readily be taken twice a day. Subjects may need to remain in the hospital longer than 3 days if two consecutive thick blood smears negative for *P. vivax* are not obtained within the 3 day timeframe.
- At the Day 1 visit subjects will be screened for G6PD deficiency by a quantitative assay and the result will be determined as a percentage of the predetermined median enzyme activity of the site. Female subjects must have a minimum G6PD assay value of 40% to be enrolled, and male subjects must have a minimum G6PD assay value of 70% to be enrolled. In addition, a minimum of 50 female subjects must be enrolled that display $\geq 40\%$ - $< 70\%$ of the site median G6PD enzyme activity.
- The status of methemoglobin, an oxidized and inactive form of hemoglobin, will be assessed at selected visits.
- An independent data monitoring committee will be established to monitor, in an unblinded manner, safety in general and females with moderate G6PD deficiency in particular. The latter will ensure the frequency and severity of any hemoglobin declines in females remains as expected and remains clinically acceptable.
- The primary analysis population will be the Microbiologic Intent To Treat (mITT) population, defined as all randomized subjects who receive at least one dose of blinded study medication and have microscopically-confirmed vivax parasitemia.

- Selected investigator centers will perform ophthalmic safety assessments at selected visits to monitor subjects for changes in the eye.
- Healthcare resource use and socio-economic impact data will be collected to characterize *P. vivax* relapse and adverse events caused by treatment to prevent *P. vivax* relapse, with particular attention to hemolytic anemia.
- Blood samples will be collected on Days 2, 3, 8, 15, 29 and 60 of the study for pharmacokinetic and pharmacodynamic analyses.

Subjects are considered to have completed the study if they meet all inclusion/exclusion criteria, are considered compliant with all study medication, complete the 3 day hospital stay, and attend the Day 180 visit.

Protocol waivers or exemptions are not allowed; therefore, adherence to the study design requirements, including those specified in the Time and Events Table, are essential and required for study conduct.

Supplementary study conduct information not mandated to be present in this protocol is provided in the accompanying Study Procedures Manual (SPM). The SPM will provide the site personnel with administrative and detailed technical information that does not impact subject safety.

3.3. Discussion of Design

The design of TAF116564 has been made purposely similar to Part 2 of sister study TAF112582, the pivotal phase III efficacy and safety study of the tafenoquine program.

The overall design of the studies is based on FDA guidance for the radical cure of malaria due to *P. vivax*. In this double-blind, double-dummy design, subjects will be screened and randomized to treatment on Day 1, and will remain in the hospital for the first 3 days of the study, or until two consecutive thick blood smears are negative for *P. vivax*, to monitor study medication compliance and infection status. Subjects will continue on treatment for the first 15 days of the study and will be monitored up to day 32 for recrudescence. Subjects will continue to be monitored up to 180 days post-randomization for evidence of relapsing infection. In all subjects, PCR analysis of *Plasmodium* species will be conducted to investigate the genetic constitution of *P. vivax* recurrences during the study.

All subjects will receive open label CQ for the first 3 days of the study to treat the blood stage of the infection. Beginning on Day 1 or Day 2, subjects will receive TQ or the active comparator, PQ, and the corresponding placebo for treatment of the liver stage of infection. Primaquine was selected as the comparator for this study as PQ plus CQ is the current standard of care for radical cure of *P. vivax* malaria in the majority of endemic countries.

3.3.1. Dose Rationale

Tafenoquine has demonstrated preliminary efficacy following 1-3 days of dosing, which is further supported by a prolonged half-life of 15-19 days. This shorter course of therapy should significantly improve compliance and thus effectiveness of relapse prevention.

Two separate exploratory clinical studies have demonstrated TQ's utility for the treatment and radical cure of *P. vivax* malaria: Study SB-252263/047 [GlaxoSmithKline Document Number [RM2007/00309/00](#)] was conducted in two parts, and tafenoquine was administered following chloroquine treatment of blood schizonts. Tafenoquine was found to be highly efficacious across the entire 500 mg to 3000 mg dose range. In study SB-252263/058 [GlaxoSmithKline Document Number [UM2004/00017/00](#)], a total dose of 1200 mg tafenoquine was administered over 3 days. Tafenoquine resulted in 100% relapse prevention, however, the tafenoquine monotherapy regimen exhibited slow parasite and fever clearance times relative to the CQ+PQ control. In conclusion, TQ's long half-life supported a 1 to 3 day treatment regimen when co-administered with a second blood schizonticidal drug, such as CQ.

A two-part drug-drug interaction study [GlaxoSmithKline Document Number [WD2009/01503/00](#); Study TAF106491] has also been conducted to investigate the interaction between TQ and CQ in healthy volunteers. Part 1 was a three arm, open label pilot study to evaluate the safety and pharmacokinetics of a low dose CQ co-administered with TQ. Part 2 was a double-blind study to assess the drug-drug interaction, safety (including ECG effects), tolerability and pharmacokinetic parameters of CQ co-administered with TQ. Based on the PK results from the pivotal Part 2 portion of this study, there appears to be a short term significant effect on TQ PK (Day 2 Cmax and AUC(0-24)) when co-administered with CQ with no significant effect on the full PK profile (AUC(0-∞) and t1/2). TQ had no significant effect on the PK of CQ and desethylchloroquine. Taken together, these results suggest that there is no clinically significant pharmacokinetic interaction with concomitant administration of TQ and CQ.

A thorough QT study (TAF114582) was recently completed that studied two therapeutic doses (300mg and 600mg; single dose) and one supratherapeutic dose (1200mg; 400mg x 3) of tafenoquine. The therapeutic doses of tafenoquine had no marked effect on QTcF prolongation. In the 1200mg group, a mean effect of 6.6 msec in QTcF prolongation was observed, just within the 10 msec safety margin set out in E14 ICH guidelines.

Throughout the tafenoquine program, subjects have been evaluated for changes in Hb following treatment with TQ. In G6PD-normal subjects only small decreases in Hb have been observed. These changes were not considered clinically significant, and were only seen in subjects receiving doses of TQ much higher than what had been considered for clinical investigation. In studies where G6PD-deficient subjects have been included, significant Hb decreases have been observed. A study was recently completed (TAF110027) that assessed the hemolytic risk of TQ in female healthy volunteers with moderate G6PD deficiency (40%-60% of site median normal value). Results indicated a TQ dose response for hemolysis, and the highest dose of TQ tested, 300mg, resulted in Hb declines similar to daily dosing of 15mg PQ. This data factored greatly into determining a dose to take forward into phase III.

Tafenoquine was recently investigated in part 1 of TAF112582, a seamless Phase II/III study. The phase II portion (part 1) was a dose-ranging study assessing the efficacy and safety of four doses of TQ in subjects with *P. vivax* malaria. The goal was to select an efficacious and well-tolerated dose of TQ to be co-administered with CQ. The long half-life of TQ allowed it to be delivered as a single dose. The 300mg dose achieved highly significant improvements ($p < 0.0001$) in relapse-free efficacy compared to CQ alone.

Treatment differences (TQ/CQ - CQ) ranged from 45% for the most conservative analyses to 61%. Small declines in Hb were seen; approximately 30% of subjects in the 300mg TQ dose experienced a decline in Hb of >1.5 g/dL and <2.5 g/dL. Only 2 (4%) subjects experienced a Hb drop >2.5 g/dL. All other treatment groups experienced similar Hb drops, and all were considered disease-related. At the conclusion of Phase II, the single 300mg dose of TQ was selected to carry forward to the Phase III program.

4. SUBJECT SELECTION AND WITHDRAWAL CRITERIA

Subjects who have a blood smear positive for a single species infection with *P. vivax* and meet all other eligibility criteria qualify for entry into the study. A total of 300 subjects will be randomized into the study, and 50 of these will be females with G6PD enzyme levels consistent with moderate G6PD deficiency. The primary study population is the mITT population, and includes all subjects who meet all eligibility criteria and receive at least one dose of blinded study medication.

4.1. Number of Subjects

Randomized: 300

Subject Screening Failures: 150

Number of Evaluable Subjects: 300

Number of Screened Subjects: 450

4.2. Eligibility Criteria

4.2.1. Inclusion Criteria

Specific information regarding warnings, precautions, contraindications, adverse events, and other pertinent information on the GSK investigational product or other study medication that may impact subject eligibility is provided in the Tafenoquine Investigator Brochure [GlaxoSmithKline Document Number [GM2007/00152/06](#)], and the locally-approved product labels for Chloroquine and Primaquine.

Deviations from inclusion criteria are not allowed because they can potentially jeopardize the scientific integrity of the study, regulatory acceptability or subject safety. Therefore, adherence to the criteria as specified in the protocol is essential.

Subjects eligible for enrolment in the study must meet all of the following criteria:

Safety

1. A female is eligible to enter and participate in the study if she is non-pregnant, non-lactating and if she is of:
 - a. Non-childbearing potential defined as: post-menopausal (12 months of spontaneous amenorrhea or <6 months of spontaneous amenorrhea with serum FSH >40 mIU/mL), or pre-menopausal and has had a hysterectomy or a bilateral oophorectomy (removal of the ovaries) or a bilateral tubal ligation, negative pregnancy test or,
 - b. Child-bearing potential, has a negative pregnancy test at screening, and agrees to comply with one of the following during the treatment stage of the study and for a period of 90 days after stopping study medication:
 - Use of oral contraceptive, either combined or progestogen alone used in conjunction with double barrier method as defined below.
 - Use of an intrauterine device with a documented failure rate of <1% per year
 - Use of depo provera injection
 - Double barrier method consisting of spermicide with either condom or diaphragm
 - Male partner who is sterile prior to the female subject's entry into the study and is the sole sexual partner for that female.
 - Complete abstinence from intercourse for 2 weeks prior to administration of study medication, throughout the study and for a period of 90 days after stopping study medication.
2. The subject has a glucose 6-phosphate dehydrogenase (G6PD) value (measured by a quantitative spectrophotometric phenotype assay) as follows:
 - **Female subjects** must have an enzyme level $\geq 40\%$ of the site median value for G6PD normal males.
 - **Male subjects** must have an enzyme level $\geq 70\%$ of the site median value for G6PD normal males.
3. The subject has a screening hemoglobin (Hb) value as follows:
 - Any subject with a G6PD value $\geq 70\%$ of the site median value must have a screening Hb value ≥ 7 g/dL.
 - Female subjects with a G6PD value is $\geq 40\%$ - <70% of the site median value must have a screening Hb value ≥ 8 g/dL.

4. The subject has a QTcF of <450 msec.

N.B. Reading based on an average of triplicate ECGs obtained over a brief recording period by machine or manual over-read.

Efficacy

5. The subject has a positive malarial smear for *P. vivax*.
6. The subject has a parasite density of >100 and <100,000/ μ L.

Other

7. Male or female subject aged 16 years or older (18 years or older in Ethiopia) at the time of signing the informed consent.
8. The subject agrees to G6PD genotyping.
9. The subject is willing and able to comply with the study protocol.
10. The subject or parent/legal guardian, as applicable, has given written informed, dated consent; and the subject has given written assent, if applicable, to participate in the study.

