	MATE2. Inhibition of these transporters may explain mild, transient, asymptomatic increases of creatinine observed in previous clinical studies and also may lead to increased exposure to medications excreted via these transporters.	
Use in pregnancy and lactation	
Preclinical data reported no adverse effects on fertility, embryofetal development or on post-natal survival.
 
No clinical studies have been conducted in humans during pregnancy. There may be concern about risk to a fetus who is G6PD deficient and risk to breastfed infants whose G6PD status may be unknown.
	Pregnant or lactating women are excluded from this study.
Phototoxicity	Preclinical studies have been conducted to assess TQ photoirritancy factor. The conclusion of these studies was that tafenoquine was “probably” phototoxic. A review of Integrated clinical safety data (>4000 subjects) has not determined any discernible pattern of incidence of rash associated with TQ treatment.	The incidence and frequency of rash will continue to be reviewed for signs of photoirritancy in this patient population.

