5.1.7. Duration of Treatment of Active Study Medication

The total duration of treatment is 15 days.

Chloroquine will be dosed orally once daily for three days starting on Day 1 of the study.

Tafenoquine will be dosed orally as a single dose on Day 1 or Day 2 of the study.

Primaquine will be given as a 14-dose course administered orally once daily for 14 days starting from Day 1 or Day 2 of the study.

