- q The pharmacogenetics sample must be collected at the earliest opportunity after randomization and during the in-clinic treatment visit (Days 1-3).
- r Serum or urine pregnancy test that is routinely used at site with a test sensitivity for hCG level ≤ 25 mIU/mL. FSH serum test only for post-menopausal females with less than 6 months spontaneous amenorrhea.
- s Refer to Section 6.5 of the protocol for details on health outcome data collection.
- t Health outcomes assessments will only be collected at these visits from subjects with confirmed parasitemia or from subjects with clinically relevant hemolysis.
- u Day 2 and Day 3 PK samples must be taken 6-12 hours and 24-48 hours post TQ dose.
- v Treatment with blinded study medication will begin on either Day 1 or Day 2.

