 - Hematology analysis will include: Hb, hematocrit (Hct), red blood cells (RBC), mean cell volume (MCV), differentiated white blood cells (WBC), platelets and reticulocytes (for conversion to absolute).
 - Clinical chemistry evaluations will include: blood urea nitrogen (BUN), serum creatinine, total and indirect bilirubin and liver chemistries (alanine aminotransferase (ALT), aspartate aminotransferase (AST), alkaline phosphatase (ALP) and creatine phosphokinase (CPK))
- A serum or urine pregnancy test will be performed that is routinely used at the site, provided the test has a sensitivity for hCG of ≤ 25 mIU/mL. A FSH serum test will be performed only for post-menopausal females with less than 6 months spontaneous amenorrhea.
- Methemoglobin levels will be assessed using a non-invasive signal extraction CO-Oximeter handheld machine.
- 12 lead ECG will be performed with the subject in a semi-supine position having rested in this position for at least 10 minutes beforehand. Measurements that deviate substantially from previous readings will be repeated immediately. Three (3) measurements will be taken at screening, five minutes apart.
 - The mean hear rate, RR interval, QRS duration, QT interval and QTcF (QT corrected by Friderica's formula) will be calculated from automated ECG readings and abnormal findings will be recorded. The mean value recorded pre-dose will be classified as baseline.
- A subset of qualified sites will perform the following ophthalmic assessments during in-patient stay and prior to randomization:
 - Visual acuity and color vision will be assessed by standard methods

- Humphrey 10-2 visual field in order to determine the threshold sensitivity of specific loci in the central retina, detection and definition of relative or absolute scotomas.
- Slit lamp examination of the cornea (to document and grade any corneal deposits), lens and retina.
- Retinal digital photography for the documentation of changes in the retinal morphology.

6.2. **Unscheduled Visits**

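### Criterion 1a frees women with under 6 months of amenorrhoea and FSH above 40 mIU/mL from contraception, while women at 6 to under 12 months remain bound by it

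*Supplement*

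**What the plan says.** Criterion 1 of section 4.2.1 (Protocol Amendment 5) admits women who are neither pregnant nor lactating and who fall under 1a (non-childbearing potential) or 1b (childbearing potential). Within 1a, post-menopausal is defined as "12 months of spontaneous amenorrhea or <6 months of spontaneous amenorrhea with serum FSH >40 mIU/mL". The other route into 1a is surgical: hysterectomy, bilateral oophorectomy or bilateral tubal ligation. A negative pregnancy test is mentioned at the end of 1a, but its placement leaves unclear whether it covers both routes or only the surgical one.

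Only 1b imposes contraception, and it does so "during the treatment stage of the study and for a period of 90 days after stopping study medication".

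Two other places carry the same interval. Section 6.1 states: "A FSH serum test will be performed only for post-menopausal females with less than 6 months spontaneous amenorrhea". Footnote r of Table 2 has "FSH serum test only for post-menopausal females with less than 6 months spontaneous amenorrhea".

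On risk, Table 1 in section 1.3.1 says "No clinical studies have been conducted in humans during pregnancy" and "There may be concern about risk to a fetus who is G6PD deficient"; the same row reports no adverse preclinical effect on fertility or embryofetal development. Section 3.3.1 gives tafenoquine a "prolonged half-life of 15-19 days", and section 5.1.7 says "Tafenoquine will be dosed orally as a single dose on Day 1 or Day 2 of the study".

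**The concern.** A rule of this kind should become easier to satisfy as the evidence of menopause grows. Here it does not. A short history with a raised FSH releases a woman from contraception, a longer history does not, and a full year does. The short limb has no stated minimum, and the protocol gives no reason for the pattern.

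What is at stake is fetal exposure. The sponsor judged contraception necessary through treatment and for 90 days afterwards, and this clause waives it where menopause is least well established. If such a woman conceives, withdrawing her cannot end tafenoquine exposure, because the whole dose has been given by Day 1 or Day 2 and clears slowly.

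**Working it through.** No sample size, power or error rate is involved and the plan states no figure to reproduce. The check is a reading of the eligibility logic, followed by a comparison of the waived contraception period with the pregnancy tests that remain.

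**Step 1. Map duration of amenorrhoea to the criterion.** Take a woman who is regarded as post-menopausal, has had no sterilising surgery and would have FSH above 40 mIU/mL if tested.

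| Spontaneous amenorrhoea | FSH measured under 6.1 and footnote r? | Criterion met | Contraception required? |
|---|---|---|---|
| Under 6 months, no stated minimum | Yes | 1a, FSH limb | No |
| 6 to under 12 months | No | Neither limb of 1a, so 1b | Yes |
| 12 months | No, and not needed | 1a, duration limb | No |

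The exemption runs yes, no, yes as duration increases.

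**Step 2. Is it corrected elsewhere?** Section 6.1 and footnote r repeat the under-6-month interval. The revision chronology and Appendix 6 list no change to this criterion. Section 4.2.1 says deviations from the inclusion criteria are not allowed, and section 3.2 allows no waivers. A careful investigator could still place such a woman under 1b, but nothing in the text requires it.

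**Step 3. What is waived.** Blinded medication ends with the last of 14 daily primaquine or placebo doses (section 5.1.7): Day 14 if started on Day 1, Day 15 if started on Day 2. Adding 90 days:

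- Start on Day 1: 14 + 90 = Day 104, which is 104 − 1 = 103 days after the tafenoquine dose.
- Start on Day 2: 15 + 90 = Day 105, which is 105 − 2 = 103 days after the dose.

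At the stated half-life, 103 days is 103/19 = 5.4 to 103/15 = 6.9 half-lives. The 90-day rule therefore covers several half-lives of the drug, and that cover is what the exempted women lose. These figures describe the length of the waived period. They do not measure how many women are affected or how likely a conception is.

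**Step 4. What remains.** The safeguards for an exempted woman are:

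- non-pregnancy at entry (criterion 1);
- pregnancy tests in Table 2 on Days 1, 15, 29, 60 and 180 and at relapse or withdrawal visits, with required sensitivity of 25 mIU/mL hCG or better and no restriction to women under 1b;
- pregnancy as a withdrawal reason (section 4.3);
- collection of pregnancies to Day 180 and follow-up to outcome (sections 6.4.8 and 6.4.8.1).

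Each of these detects or follows a conception. None prevents one. After Day 60 the next routine test is at Day 180, so the last part of the waived period, from Day 60 to Day 104 or 105, contains no scheduled test.

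**The case against.** The strongest reply is that the clause reaches few women, and much of that reply stands.

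- **FSH is not measured freely.** Section 6.1 and footnote r call for it only in women already regarded as post-menopausal. A woman with missed periods whom the clinician considers pre-menopausal has no protocol FSH test and so no protocol route into this limb. A reader might infer that every woman with a high FSH and any history down to 0 months is released; the text does not support that, and 0 months is not amenorrhoea. The gate is clinical judgement, however, not a minimum duration, so it narrows the gap without closing it.
- **The 6 to under 12 month band is not at risk.** Those women fall to 1b, the stricter arm. Their treatment shows that the rule is inconsistent; it exposes nobody.
- **Surveillance is real.** A reader might infer that exempted women go unmonitored. Table 2 schedules repeat tests for them, as set out above. Those tests find pregnancies after the fact.
- **Slow clearance does not size the defect.** A reader might take the half-life as a measure of fetal risk from this clause. It applies to any tafenoquine-treated woman and says nothing about how many are exempted or conceive. It matters only in that withdrawal cannot undo the exposure.
- **The preclinical findings are reassuring.** They sit in the same risk table as the concern for a G6PD-deficient fetus, and the sponsor still required contraception under 1b.

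**Conclusion.** The point holds as a fault in an operative eligibility rule. As written, a woman regarded as post-menopausal with less than 6 months of amenorrhoea and FSH above 40 mIU/mL is excused from contraception, although hers is the weakest evidence of menopause of any group admitted through the post-menopausal definition. The two FSH testing rules repeat the interval.

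The consequence is limited to participant safety. The documents give no count of women affected; it is probably small, and no probability of conception or fetal harm can be derived from them. No endpoint, population or analysis changes. The change is worth making because it closes an avoidable gap in fetal protection at little cost.

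A reader might conclude that the inequality was simply reversed and that at least 6 months was meant. That is plausible, but no section says so, and the same interval appears in all three places. The intended threshold has to come from the sponsor.

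**What to change.** Delete the limb with under 6 months of amenorrhoea and raised FSH from criterion 1a, so that these women fall under 1b unless surgically sterile. Make 12 months of spontaneous amenorrhoea the default definition of post-menopausal. Remove or align the FSH testing rules in section 6.1 and Table 2 footnote r. This default releases no woman whom 1b now covers.

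Ask the sponsor which interval was intended. Only if the answer is at least 6 months should the FSH route be restated as 6 to under 12 months of spontaneous amenorrhoea with FSH above 40 mIU/mL, in all three places.

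The cost is a small text change that can be bundled with another amendment, with the ethics committee approval that section 9.2 requires, and contraception for a few peri-menopausal women. If the sponsor confirms the longer interval, a few women at 6 to under 12 months with raised FSH would leave 1b.
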